5.2.3.2 Flush pressure profile

Manual flush variability will be evaluated using duration of flush and characteristics of Flush pressure profile obtained on in-line pressure measurements. They will be comprised of:

- Peak pressure
- Flush duration (sec.)

For each of these characteristics, summary statistics by indwell time considered as a discrete variable (0, 6, 24, 30, 48, 54, 72 hours) and longitudinal line and bar plots will be generated on average for continuous and by proportion for categorical responses, respectively.

Lineplots will be similar to the example provided for cfHb in Figure B.3.2 and bar plots will be similar to the example provided for Haemolysis occurrence in Figure B.4.1, both represented in Appendix B.

Relationship between the occurrence of these events will be investigated using the Boruta algorithm with a survival random forest model (an example output from the algorithm is provided in the Appendix by Figure B.7.1) where the variables coding for these events will be predictors.

Based on the outcome of the Boruta algorithm, models might be used to investigate further the relationship between these variables and indwell time.

5.2.4 General Considerations

- For categorical data, count and percentage with 95% confidence interval will be calculated.
- For continuous data, average, standard error, 95% confidence interval, median, inter-quartiles, minimum and maximum will be provided.
- p-values less than 0.05 will be considered statistically significant. Multiple comparisons adjustments (Tukey's or Sydak's) will be made when appropriate
- Importance of factors/variables might be evaluated using machine learning tools such as the Boruta algorithm (random forest all-relevant approach)

- Whenever possible, effects of the following covariates will be investigated: gender, age and BMI
- Initially, all factors/variables will be included into the model as well as any two-way/three-way interactions.
- Variables or interactions which are not significant ($p\text{-value} < 0.05$) will be removed from the final model. Models adjusted with significant effects (and significant interactions if any) will be used for analysis whenever possible.
- Use of models will be preferred to non-parametric tests whenever possible.
- Residual plots for each model will be drawn and reviewed to ensure there are no systematic patterns.
- Transformation of response and/or explanatory variables will be investigated whenever modeling assumptions are not satisfied.

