4 STUDY DESIGN

4.1 Overall Design

This is a randomized, single-center, open-label feasibility trial to provide preliminary signals of performance to help make decisions about whether to continue with the development of product enhancements. Four variations of the BD Nexiva PIVC (20G x 1, 20G x 1.75, 22G x 1, or 22G x 1.75) will be placed in the lower cephalic vein of both arms in approximately 40 healthy volunteers; 20 participants with 20G x 1 inch and 20G x 1.75 inch catheters, and second group of 20 participants with 22G x 1 inch and 22G x 1.75 inch catheters. PIVC indwell time will be monitored (removal at 72 hrs or upon inability to flush/aspirate) with blood collected by venipuncture (Day 1 only) and via the devices using 2 and 6mL vacutainers throughout the remainder of indwell time.

After 5 participants have completed their final visit, the in-situ catheter positions will be compared to the expected tip position based on the catheter lengths (1 inch versus 1.75 inch for either gauge). Tip position of the longer catheter is expected to reside more horizontally within the vessel. In the event catheter tip position differences are not distinct between catheter device lengths study conduct may be stopped. Additionally, this analysis will be used to refine study logistics associated with device placement, securement, sonographic measurements, and blood sample acquisition/testing over the 72-hour study duration.

Each participant will complete 6 visits: a Screening Visit (V1), followed by 4 Visits (V2-V5) to be started within 30 days after screening, and a 24-96 hour follow-up post catheter removal (V6).

The duration of the study execution is expected to be 5 months.

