10.8 Other Analyses

Descriptive statistics (number of observations, mean, standard deviation, minimum, maximum and 95% mean confidence interval) will be calculated and presented for all quantitative responses (e.g., medical history questionnaire responses). Frequency tables with number of observations, percentage of total and 95% confidence interval for the percentage (as applicable) will be created for discrete responses.

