5.2 Analysis Methods

The following section defines hypothesis that will be tested. However, given the feasibility nature of the study no acceptance criteria were defined and estimating absolute effects and statistical significance of difference between device configuration is of similar importance.

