5.2.1 Statistical Analysis of Primary Endpoint

5.2.1.1 Indwell Time

It is hypothesized that:

- PIVC indwell time will be greater for longer catheters
- PIVC indwell time will be greater for catheters of smaller gauge (larger bore)

In order to test these hypotheses, catheter indwell time will be assessed using survival analysis, including:

- Kaplan-Meier survival curves including Log-Rank test p-value
- Cox Proportional Hazards Model with Hazard Ratios for each device vs. default device condition (BD Nexiva 20G x 1 inch) and associated 95% Confidence Intervals. Effect of the following covariates will be investigated: gender, age, BMI and dominant arm.

Main analysis will be performed stratified by device, depending on the results pooled analyses by gauge or by catheter length might be performed. An example of the Kaplan-Meier curve and associated metrics is provided in Appendix B by Figure B.1.1. An example of the Hazard Ratios extracted from the Cox Proportional Hazards models is provided in Appendix A by Table A.4.2.

For the purpose of this survival analysis, device failure (inability to flush or draw blood, see section 6.6) will be identified as follows:

- Blood Draw: Variables DEBLDCS equal to “N” and DEBLDRS equal to “N” from table INBCINBC
- Flush: Variables DEFLSSU equal to “N” and DEFLSRS equal to “N” from table INFL

Failure can occur during any of the 7 repeats of the blood draw (for either tube volumes) or flush processes, as highlighted in orange on Table 2.7.1, for right or left arm, per randomization schedule. Date-time of failure is then given by the aggregation of variables DEDTN & DEFTM, from tables INBCINBC or INFL, respectively for blood draw or flush.

Additional Indwell Time summary statistics and graphical representation will be provided as represented in Appendix A by Table A.4.1 and in Appendix B by Figure B.2.1, respectively.

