Table A.9.1: Numerical Summary of Blood Draw Fill Time in seconds for each Vacutainer tube, per Device Configuration (Gauge and Length) and Overall

tube	Characteristic	BD Nexiva (22G x 1 inch)	BD Nexiva (22G x 1.75 inch)	BD Nexiva (20G x 1 inch)	BD Nexiva (20G x 1.75 inch)	Overall
2mL	Blood Draw Fill Time (sec)					
	Mean	59.30	60.29	59.53	60.95	60.10
	95% Mean CI	58.23, 60.33	59.36, 61.20	58.67, 60.39	60.06, 61.82	59.64, 60.57
	Median	59.27	60.16	59.37	61.52	60.00
	SD	5.08	4.91	4.82	5.25	5.05
	Min, Max	45.83, 72.19	46.29, 73.76	46.69, 70.86	48.88, 77.06	45.83, 77.06
	Total Count	88	109	117	135	449
6mL	Blood Draw Fill Time (sec)					
	Mean	100.29	100.60	99.14	98.97	99.67
	95% Mean CI	98.90, 101.73	99.15, 101.98	97.77, 100.49	97.83, 100.16	98.99, 100.33
	Median	99.29	101.14	99.48	97.99	99.33
	SD	6.74	7.44	7.37	6.90	7.14
	Min, Max	84.03, 118.89	82.55, 118.55	84.03, 115.48	84.56, 119.35	82.55, 119.35
	Total Count	85	106	114	131	436

Table A.9.2: Numerical Summary of Blood Draw Fill Time in seconds for each Vacutainer tube, for each time point, per Device Configuration (Gauge and Length) and Vacutainer tube and Overall

Tube	Time Point (hours)	Characteristic	BD Nexiva (22G x 1 inch)	BD Nexiva (22G x 1.75 inch)	BD Nexiva (20G x 1 inch)	BD Nexiva (20G x 1.75 inch)	Overall
2mL	0	Blood Draw Fill Time (sec)					
		Mean	58.77	61.25	60.41	59.01	59.86
		95% Mean CI	57.34, 60.13	59.28, 63.32	58.37, 62.49	56.57, 61.52	58.83, 60.89
		Median	58.92	61.46	60.54	58.64	59.34
		SD	3.29	4.70	4.87	5.69	4.74
		Min, Max	51.27, 63.83	53.66, 70.59	51.38, 69.45	49.33, 69.93	49.33, 70.59
		Total Count	20	20	20	20	80
2mL	6	Blood Draw Fill Time (sec)					
		Mean	60.94	58.40	58.76	62.05	60.04
		95% Mean CI	59.21, 62.74	56.21, 60.58	57.19, 60.43	59.89, 64.32	59.03, 61.09
		Median	59.90	59.05	58.06	62.15	59.43
		SD	3.98	4.94	3.79	5.22	4.70
		Min, Max	53.83, 68.83	46.29, 69.44	52.58, 65.84	52.49, 75.85	46.29, 75.85
		Total Count	18	19	20	20	77
2mL	24	Blood Draw Fill Time (sec)					
		Mean	56.85	60.95	58.56	60.95	59.41
		95% Mean CI	54.47, 59.10	58.49, 63.48	57.07, 60.08	58.34, 63.31	58.23, 60.56
		Median	58.67	61.31	58.66	62.31	59.64
		SD	4.92	5.57	3.54	5.82	5.21
		Min, Max	48.08, 64.9	52.09, 72.58	50.83, 66.75	48.88, 68.39	48.08, 72.58
		Total Count	16	18	20	20	74
2mL	30	Blood Draw Fill Time (sec)					
		Mean	61.60	59.05	59.24	60.83	60.12
		95% Mean CI	58.68, 64.23	57.27, 60.80	57.19, 61.40	58.69, 63.00	58.99, 61.22
		Median	61.98	59.51	58.57	60.79	60.00
		SD	5.35	3.74	4.81	5.12	4.79

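### SAP 5.2.4 sets no unit of analysis for its 95% confidence intervals, and the time-pooled Table A.9.1 shell prints intervals as wide as if every draw were independent

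*SAP*

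**What the plan says.** SAP 5.2.4 sets the summary statistics for every endpoint. For continuous data: "For continuous data, average, standard error, 95% confidence interval, median, inter-quartiles, minimum and maximum will be provided". For categorical data: "For categorical data, count and percentage with 95% confidence interval will be calculated". Protocol 10.8 is to the same effect; for frequency tables, a "95% confidence interval for the percentage (as applicable) will be created for discrete responses". None of these passages gives a formula, a unit of analysis or a rule for several values from one catheter or participant.

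The mock tables are the only guide to how the intervals will be built. Table A.9.1 is headed "Numerical Summary of Blood Draw Fill Time in seconds for each Vacutainer tube, per Device Configuration (Gauge and Length) and Overall". It has no time dimension, and its 2 mL count row reads "Total Count 88 109 117 135 449". Those are draws. Protocol 4.1 places "20 participants with 20G x 1 inch and 20G x 1.75 inch catheters" in the first group, with a matching 22G group, so each device column rests on 20 catheters. SAP 5.2.1.1 confirms the repetition: "Failure can occur during any of the 7 repeats of the blood draw".

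For comparing devices on fill time, SAP 5.2.2.2 specifies a linear mixed model with a random subject effect.

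**The concern.** Up to seven fill times from one catheter, in one vein of one person, are unlikely to be independent. The plan itself leans this way. Protocol 4.2 justifies the paired design by variability between participants, and SAP 5.2.2.2 gives fill time a subject effect. An interval computed from the number of draws ignores this and claims more precision than 20 catheters can supply.

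The intervals carry some weight because SAP 2.9 sets no acceptance criteria and SAP 5.2 says that "estimating absolute effects and statistical significance of difference between device configuration is of similar importance". A reader may set the four device intervals in A.9.1 side by side. Longer-lasting devices give more draws per catheter, so the understatement would also differ between the columns being compared.

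**Working it through.** **Inputs.** SDs, counts and limits are from SAP Table A.9.1; counts by time point from A.9.2; 20 catheters per device from Protocol 4.1. The ICC is in neither document and is an assumption.

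**Step 1: reproduce the printed widths.** Half-width = 1.96 x SD / sqrt(draws).

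| Tube, device | Draws | SD | Printed | By formula |
|---|---|---|---|---|
| 2 mL, 22G x 1 | 88 | 5.08 | 1.050 | 1.061 |
| 2 mL, 22G x 1.75 | 109 | 4.91 | 0.920 | 0.922 |
| 2 mL, 20G x 1 | 117 | 4.82 | 0.860 | 0.873 |
| 2 mL, 20G x 1.75 | 135 | 5.25 | 0.880 | 0.886 |
| 6 mL, 22G x 1 | 85 | 6.74 | 1.415 | 1.433 |
| 6 mL, 22G x 1.75 | 106 | 7.44 | 1.415 | 1.416 |
| 6 mL, 20G x 1 | 114 | 7.37 | 1.360 | 1.353 |
| 6 mL, 20G x 1.75 | 131 | 6.90 | 1.165 | 1.182 |

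All eight agree within about 2%. Dividing instead by sqrt(20) would give 1.96 x 5.08 / sqrt(20) = 2.23 s in the first row.

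**Step 2: draws per catheter.** For 22G x 1 inch, 2 mL, the A.9.2 counts from 0 to 72 h are 20, 18, 16, 13, 9, 6, 6, which sum to 88. If a catheter that drops out does not return, 2, 2, 3, 4, 3, 0 and 6 catheters give 1, 2, 3, 4, 5, 6 and 7 draws. Cluster sizes are unequal, so the relevant size is m = (sum of squares) / (sum) = (2 + 8 + 27 + 64 + 75 + 0 + 294) / 88 = 470 / 88 = 5.34, not the plain mean of 88 / 20 = 4.40.

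**Step 3: widening and coverage.** Design effect DE = 1 + (m - 1) x ICC. The half-width grows by sqrt(DE), and true coverage is 2 x Phi(1.96 / sqrt(DE)) - 1. For 22G x 1 inch at ICC 0.3, DE = 1 + 4.34 x 0.3 = 2.30, the factor is 1.52, and 1.06 s becomes 1.61 s.

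| 2 mL | m | ICC 0.1 | ICC 0.3 | ICC 0.5 |
|---|---|---|---|---|
| 22G x 1 | 5.34 | 1.20 (90%) | 1.52 (80%) | 1.78 (73%) |
| 22G x 1.75 | 6.05 | 1.23 (89%) | 1.59 (78%) | 1.88 (70%) |
| 20G x 1 | 6.13 | 1.23 (89%) | 1.59 (78%) | 1.89 (70%) |
| 20G x 1.75 | 6.79 | 1.26 (88%) | 1.65 (76%) | 1.97 (68%) |

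The 6 mL factors are 1.19-1.25, 1.50-1.64 and 1.76-1.95. Simulating the 22G x 1 inch, 2 mL pattern (20,000 runs) gave coverage of 94%, 89%, 80% and 72% at ICC 0, 0.1, 0.3 and 0.5, in line with the formula.

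**Step 4: Table A.10.1.** It pools 98, 116, 124 and 138 thrombus observations from 20 catheters per device and prints no interval, though 5.2.4 calls for one. For 20G x 1.75 inch, 68/138 = 49.3%. Counting observations, the half-width is 1.96 x sqrt(0.493 x 0.507 / 138) = 8.3 points. In the limiting case where thrombus status never changes within a catheter, effective n is about 20 and the half-width is about 22 points.

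**Step 5: Overall columns.** A.8.1 at 0 h has 160 samples from 40 participants (two arms, two tubes): half-width 5.87 printed, 5.97 from n = 160. A.4.1 has 80 catheters from 40 participants: 4.21 printed, 4.16 from n = 80. With one common within-participant correlation of 0.1, 0.3 or 0.5, the factors would be sqrt(1 + 3 x ICC) = 1.14, 1.38, 1.58 and sqrt(1 + ICC) = 1.05, 1.14, 1.22.

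**Step 6: cells that are clean.** Device columns of A.4.1, A.8.1 and A.9.2 hold at most one value per catheter per cell (for example n = 20 per device at 0 h), so repeated draws cannot narrow them.

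**The case against.** - **The wording of 5.2.4 is neutral, and the shells are dummy data.** This is true. The printed limits are also asymmetric (A.4.1 Overall: 57.54 with limits 53.19 and 61.60, so -4.35 and +4.06). Only the width is reproduced, and the exact method is unknown.
- **The dummy draws look uncorrelated.** In A.9.4 at 0 h, 2 mL, a within-participant contrast and a between-participant contrast have nearly equal half-widths (4.99 and 5.00). The mock data therefore cannot supply an ICC, and a clustered method run on them would give much the same width. What stands is that the SAP names no such method for its summary intervals and the shell counts only draws, so a programmer following both would produce draw-level intervals on the real data.
- **Inference is handled elsewhere.** This stands. Device differences in fill time come from the mixed model, the A.9.4 contrasts and Figures B.5.2 and B.5.4. Table A.9.1 tests nothing, and fill time is a secondary endpoint.
- **Scope.** A reader might infer that all the summary tables are affected. Step 6 shows that they are not. A reader might also infer from Table 2.7.1, which schedules scans before and after each access, that the ultrasound summaries pool both. The shells do not support that: A.10.2 shows 20 observations per device at 0 h, one per catheter.

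**Conclusion.** The point holds for a limited set of cells: the device and Overall columns of A.9.1, any interval added to A.10.1, and Overall columns that combine arms or tubes, as in A.4.1 and A.8.1. For A.9.1, 2 mL, the intervals are too narrow by a factor of 1.20-1.26 at ICC 0.1, 1.52-1.65 at 0.3 and 1.78-1.97 at 0.5. This rests on an assumed positive ICC common to the devices, and on drop-out without return. At ICC 0 there is no shortfall, so it would be wrong to say outright that coverage is below 95%.

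A reader might conclude that the indwell-time result or the device comparisons are compromised by these intervals. The documents do not support that: the log-rank and Cox analyses and the mixed-model contrasts do not use them. This is a defect of descriptive precision on secondary endpoints, worth correcting because it is cheap.

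**What to change.** - In SAP 5.2.4, state the unit of analysis. Where a cell holds more than one value per participant, take the interval, for means and percentages alike, from a participant-level (cluster) bootstrap, a cluster-robust estimate or a mixed-model marginal estimate. Resampling participants covers correlation within a catheter and between arms; a mixed model with only a subject effect may miss the catheter level.
- Apply this to the A.9.1 and A.10.1 shells and to Overall columns that combine arms or tubes. Leave the device columns of A.4.1, A.8.1 and A.9.2 as they are.
- For A.4.1 Overall, use the cluster bootstrap or omit the interval. A mixed-model mean is unsuitable because indwell time is censored at 72 h.
- In these cells, print the numbers of catheters and participants beside the number of draws or observations.

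The cost is SAP wording and table code, with no change to data collection. The downside is wider printed intervals.

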3. Rate of occurrence measured using the results of the AU480 Analysis at each time point listed in red in Table 2.7.1. Samples will be considered positive for haemolysis for AU480 output of + (50-99mg/dL), ++ (100-199mg/dL), +++ (200-299mg/dL), ++++ (300-500mg/dL) and +++++ (>500mg/dL), i.e. anything different from N (<50mg/dL)². A logistic mixed effect model will be used with haemolysis occurrence as response and subject as random effect. Time, gauge, length, vacutainer volume and baseline (at D1.2) cfHb will be fixed effects. Examples of the table summarizing occurrence rates per device per time point and associated graphical representation are provided in Appendix A by Table A.10.2 and in Appendix B by Figures B.4.1 and B.4.2, respectively. Contrast based multiple comparisons will be used to compare haemolysis rate between conditions (between gauge, between length) at each timepoint.
4. Rate of occurrence measured using the results of the visual assessment at each time point listed in red in Table 2.7.1. Samples will be considered positive for haemolysis for visual values $\geq 50\text{mg/dL}$, as shown on the reference chart. A logistic mixed effect model will be used with visually observed haemolysis occurrence as response and subject as random effect. Time, gauge, length, Vacutainer tube volume and baseline (at D1.2) cfHb will be fixed effects. An example of the table summarizing occurrence rates per device per time point is provided in Appendix A by Table A.10.2. Graphical representation will be similar to the ones given as example for the AU480 analysis. Contrast based multiple comparisons will be used to compare haemolysis rate between conditions (between gauge, between length) at each timepoint.

In each case, i.e. for cfHb, AU480 and visual assessment, modeling will be preceded by an assessment of the importance of potential covariates using the Boruta algorithm. The covariates of interest will include,

¹A separate assessment of the relationship between the cfHb and AU480 measurements will be performed in order to check the validity of this threshold, which could be modified upon review of these results.

²A separate assessment of the relationship between the cfHb and AU480 measurements will be performed in order to check the validity of this threshold, which could be modified upon review of these results.

but will not be limited to:

- Presence of thrombus
- Size of thrombus
- Proximity of thrombus to tip of catheter
- Draw rate

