5.2.2.2 Blood draw fill time

It is hypothesized that:

- The blood draw duration observed for blood samples (all vacutainers, at all timepoints) collected from shorter catheters will be decreased when compared to longer catheters of the same gauge.
- The blood draw duration observed for blood samples (all vacutainers, at all timepoints) collected from smaller gauge (larger bore) catheters will be decreased when compared to larger gauge (smaller bore) catheters of the same length, over time.
- The blood draw duration observed for blood samples (all catheters, at all timepoints) collected into greater volume vacutainers will be increased when compared to smaller volume vacutainers.

A linear mixed effect model will be used with blood draw fill time as response and subject as random effect. Time, device configuration (gauge, length and their interaction), Vacutainer tube volume and baseline (at D1.2) blood draw fill time will be fixed effects. Contrast based multiple comparisons will be used to compare blood draw fill time between conditions (between gauge, between length) at each timepoint. Example tables for summary statistics (overall and per time point for each Vacutainer tube volume are given in the Appendix section by Table A.9.1 and Table A.9.2, respectively. Graphical representations of distribution of blood draw time per device is provided in Figure B.5.1 and of average blood draw time is shown in the Appendix section by Figure B.5.3. Example tables for ANOVA tables (Table A.9.3) and multiple comparisons (Table A.9.4) can be found in the Appendix A

5.2.2.3 Relationship between catheter blood draw patency indwell time and presence of intra/extravenous thrombi, thrombus length, thrombus type catheter angle/tip location *in situ*, catheter length in vessel, vein depth from skin surface, C/V ratio, and vessel anatomy

Relationship, if any, will be assessed through the computation of:

1. Summary statistics stratified by indwell time considered as a discrete variable (0, 6, 24, 30, 48, 54, 72 hours)
2. Scatter plot showing time between initial Thrombus observation to time of removal per Device Configuration
3. Bar plot showing percentage of thrombus for each time point per device configuration
4. Scatter plot showing thrombus length as a function of time grouped by device configuration
5. Relationship between flush technique and presence of Thrombus

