Line plots will be similar to the example provided for cfHb in Figure B.3.2 and bar plots will be similar to the example provided for Haemolysis occurrence in Figure B.4.1, both represented in Appendix B.

Mixed effect models will be used with corresponding response and subject as random effect. Time, gauge, length, Vacutainer tube volume and baseline measurement of response will be fixed effects. Depending on the type of the response variable, the models will be:

- Linear: C/V ratio, catheter length, catheter insertion angles and blood flow velocity
- Logistic: Tip positions

Depending on model results, contrast based multiple comparisons will be used to compare means between conditions (between gauge, between length) at each timepoint. Results will be provided in Tables similar to the example given for Blood Draw Fill time in Tables A.9.3 and A.9.4, as can be found in the Appendix A.

The relationship between C/V ratio and Blood Draw Time as well as between C/V ratio and Blood Flow Velocity will be investigate using relevant graphical representation (scatter plots) and measure of association.

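### SAP 5.2.4 removes non-significant model terms without exempting device, gauge or length, which conflicts with device hazard ratios and contrasts that the SAP promises without condition

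*SAP*

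**What the plan says.** SAP 5.2.4 sets one model-building rule for all endpoints. The start is: "Initially, all factors/variables will be included into the model as well as any two-way/three-way interactions". Terms that are not significant are then removed, and: "Models adjusted with significant effects (and significant interactions if any) will be used for analysis whenever possible". No term is named as protected. (The parenthesis that defines non-significance prints the inequality the wrong way round; this is a wording slip.)

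The endpoint sections commit to outputs that need the design terms:

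- SAP 5.2.1.1 (primary endpoint): "Cox Proportional Hazards Model with Hazard Ratios for each device vs. default device condition", with 95% CIs.
- SAP 5.2.2.1, items 2 to 4: "Contrast based multiple comparisons will be used to compare haemolysis rate between conditions (between gauge, between length) at each timepoint".
- SAP 5.2.2.2: "Contrast based multiple comparisons will be used to compare blood draw fill time between conditions (between gauge, between length) at each timepoint".

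None of these depends on significance. SAP 5.2.2.4 shows that the authors can write a condition when they want one: "Depending on model results, contrast based multiple comparisons will be used to compare means between conditions (between gauge, between length) at each timepoint". The end of SAP 5.2.2.1 limits significance-based retention to covariates, but only for the haemolysis models.

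SAP 5.2 states the aim: "estimating absolute effects and statistical significance of difference between device configuration is of similar importance".

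**The concern.** Read as written, 5.2.4 tells the analyst to delete a device, gauge or length term whose p-value is 0.05 or more. The endpoint sections tell the same analyst to report estimates for that term. Two analysts who both follow the SAP could therefore produce different main tables.

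Two further effects follow. First, even if device stays, removing its interaction with time makes each fitted contrast the same at every timepoint, so the planned timepoint comparisons lose their content. Second, an estimate reported only when it is significant is biased away from the null, and its p-value and interval ignore the selection. Protocol 4.1 describes a feasibility trial whose signals inform decisions on product development, so the size of each effect with its uncertainty is the main product. A rule that removes inconclusive estimates works against that.

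**Working it through.** **1. The mock tables.** The p-values for the device terms in SAP Table A.9.3 follow from the printed chi-squares:

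- device: 2.21 on 3 df, p = 0.53
- timepoint by device: 14.15 on 18 df, p = 0.719
- device by tube: 2.76 on 3 df, p = 0.43
- timepoint by device by tube: 13.80 on 18 df, p = 0.742

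Timepoint (p = 0.372) and timepoint by tube (p = 0.532) are also non-significant. On these printed p-values the rule leaves only tube. Table A.9.4 nevertheless prints 6 device pairs x 7 timepoints x 2 tubes = 84 contrasts.

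**2. The SAP's own planning figure.** SAP 2.4 gives medians of 1 and 3 days, 3 days of follow-up, 19 + 20 catheters, two-sided alpha 0.05 and power 0.8054. With exponential times the failure probabilities are 1 - exp(-3 ln 2) = 0.875 and 1 - exp(-ln 2) = 0.500. Expected failures are 19 x 0.875 + 20 x 0.5 = 26.6. Schoenfeld's formula with HR 1/3 gives power 0.809, which agrees closely with the SAP, so these inputs were used below.

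**3. How often the Cox device term would be deleted.** Assumptions: 80 catheters (20 per device), exponential times, 1-inch median 24 h in both gauges, no gauge effect, censoring at 72 h, catheters treated as independent, likelihood-ratio test at 0.05. The first column has device alone (3 df; 2,000 trials per row). The second has device plus gender, age, BMI and dominant arm as main effects with backward elimination (1,000 trials per row). Only the HR of 0.33 comes from the SAP.

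| True length HR | Deleted, device alone | Deleted, with covariates | Median HR (20G, 1.75 v 1 inch), all trials | Same, trials where device survives |
|---|---|---|---|---|
| 0.33 | 7% | 5% | 0.32 | 0.31 |
| 0.5 | 38% | 41% | 0.49 | 0.42 |
| 0.6 | 62% | 61% | 0.60 | 0.46 |
| 0.7 | 80% | not run | 0.71 | 0.48 |
| 1 | 94% | 94% | 1.00 | not meaningful |

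Monte Carlo error on the 41% is about 3 points either way. With a 1-inch median of 48 h there are fewer failures and deletion is more frequent: 18% at HR 0.33 and 55% at HR 0.5 (500 trials each, with covariates).

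**4. The starting model taken literally.** Device (3 df) and four 1-df covariates give 3 + 4 = 7 main-effect df, 12 + 6 = 18 two-way df and 18 + 4 = 22 three-way df, in total 47. At the planning effect for length, in both gauges, expected failures are 40 x 0.875 + 40 x 0.5 = 55, or 55/47 = 1.2 per df. Such a model can barely be fitted.

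**The case against.** The best defence is that 5.2.4 is a general section, hedged, and that the specific sections govern. The haemolysis and fill-time sections list time, gauge, length (or device configuration) and tube volume as fixed effects. The mock tables keep device at p = 0.53, label it non-significant and print its contrasts. Table A.4.2 prints HRs for two devices with individual p-values of 0.175 and 0.141. This is good evidence that the authors intend to keep device terms. It does not remove the conflict: no sentence gives the specific sections priority, the hedge names no protected term and no criterion, and 5.2.4 includes all factors only at the start. Table A.4.2 shows no clash, because its overall device p-value is 0.002 and the term would survive.

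Two stronger readings are tempting and are not supported.

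- A reader might infer from Table A.9.3 that a real fill-time difference would usually be lost. The printed device line is close to a test in one reference cell (hour 0, 2 mL). If all terms were removed in one pass on such tests, a true 2 s length difference would lose device in about 80% of trials. No section specifies one-pass removal. Ordinary backward elimination that respects hierarchy deletes device in only about 1-2% at that difference.
- A reader might try to quantify the damage from the fully interacted Cox model. The SAP does not state that device-by-covariate terms belong in that model, nor whether elimination respects hierarchy. In simulation only 19% to 40% of data sets gave a stable starting fit. Rates from that model should not be relied on.

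It is also fair that the HRs of 0.5 to 0.7 are assumed, that deletion is uncommon at the planning effect, and that this is a feasibility study without acceptance criteria.

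**Conclusion.** The conflict is real and rests on the text alone. SAP 5.2.4 removes non-significant terms without exempting the design factors. SAP 5.2.1.1, 5.2.2.1 (items 2 to 4) and 5.2.2.2 promise estimates of those factors without condition, and SAP 5.2 gives estimation similar weight to significance. It should be fixed before analysis.

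The size is illustrative. In a main-effects Cox model with a 24 h median for 1-inch catheters and independent catheters, the device term and all its HRs would be deleted in about 5-7% of trials at HR 0.33, about 40% at 0.5, about 60% at 0.6 and about 94% with no effect. Within-participant correlation is ignored.

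The following are not affected: Kaplan-Meier and log-rank, the descriptive summaries, and the contrasts of SAP 5.2.2.4, which are conditional by design. The continuous cfHb model (SAP 5.2.2.1, item 1) promises no contrasts, so it does not have this conflict.

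**What to change.** Add to SAP 5.2.4:

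- Device (or gauge and length) terms, and the interactions needed for the planned contrasts, stay in every model and are reported with estimate and 95% CI whatever their p-value.
- Significance-based removal applies only to covariates and other interactions. Gender, age, BMI and dominant arm enter as main effects. Any other interaction search is labelled exploratory.
- In the logistic mixed models, if sparse or zero cells make a timepoint interaction non-estimable, the gauge and length main effects are kept and the timepoint comparisons are reported descriptively or from a penalised fit. Mock Table A.8.1 shows why: 20G x 1.75 inch has no AU480-positive sample in either tube at 24, 48, 54 and 72 h.
- The parenthesis defining non-significance reads p-value >= 0.05.

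The retention rules for baseline cfHb and the Boruta covariates, and the conditional contrasts of 5.2.2.4, can stay as they are.

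The cost is a few lines of text, with no change to data or sample size. The price is less freedom to follow unexpected interactions in the main tables, somewhat wider intervals from retained non-significant terms, and the extra fallback for sparse logistic models.
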